7.7. Concomitant Therapy

Concomitant medications with the potential to affect cognition will be permitted, provided the patient has been maintained on a stable dose regimen for at least 30 days before screening, and between screening and randomization. After randomization, attempts should be made to maintain stable doses of symptomatic AD medication, however, changes or additions will be permitted when clinically indicated and must be documented in eCRF.

The following concomitant therapies are prohibited:

- Use of any investigational drug or device not specified in this study judged to be scientifically or medically incompatible with this study
- Use of any drug of abuse, including but not limited to cannabis, illicit amphetamine, cocaine, illicit opiates, propoxyphene, methadone, methaqualone, phencyclidine, or illicit barbiturate
- Use of depigmenting agents, such as, hydroquinone
- Current use of strong inducers of CYP3A (See the Manual of Operations for a list of excluded drugs)
- Current use of drugs known to significantly prolong the QT interval (See the Manual of Operations for a list of excluded drugs)

The list of other excluded medications and procedures is provided in the Manual of Operations.

7.8. Treatment after the End of the Study

7.8.1. Continued Access

Investigational Product will not be made available to patients after conclusion of the study.

8. Discontinuation Criteria

8.1. Discontinuation from Study Treatment

8.1.1. Permanent Discontinuation from Study Treatment

Discontinuation of the investigational product for abnormal liver tests **should be considered** by the investigator when a patient meets one of the following conditions after consultation with the Lilly-designated medical monitor:

- alanine aminotransferase (ALT) or aspartate aminotransferase (AST) >8X upper limit of normal (ULN)
- alanine aminotransferase or AST >5X ULN for more than 2 weeks
- alanine aminotransferase or AST >3X ULN and total bilirubin level (TBL) >2X ULN or prothrombin time >1.5X ULN
- alanine aminotransferase or AST >3X ULN with the appearance of fatigue, nausea, vomiting, right upper-quadrant pain or tenderness, fever, rash, and/or eosinophilia (>5%)
- alkaline phosphatase (ALP) >3X ULN
- alkaline phosphatase >2.5X ULN and TBL >2X ULN
- alkaline phosphatase >2.5X ULN with the appearance of fatigue, nausea, vomiting, right quadrant pain or tenderness, fever, rash, and/or eosinophilia (>5%)

In addition, patients will be discontinued from the investigational product in the following circumstances:

- Patient decision. The patient may discontinue treatment, without prejudice to further treatment, at any time.
- Adverse event or clinically significant laboratory value, ECG result, physical examination finding (including eye or skin examination), MRI finding (such as symptomatic vasogenic edema), C-SRSS result, or vital sign measurement of such severity that, in the opinion of the investigator or Lilly-designated medical monitor, continued treatment is not in the best interest of the patient.
- Severe non-compliance to the study protocol that results in a safety concern, in the judgment of the investigator.
- The patient, for any reason, requires a treatment with an excluded therapeutic agent and temporary discontinuation criteria cannot be met (see Section 8.1.2).
- The patient develops a significant uncontrolled medical condition that meets one of the exclusion criteria that in the opinion of the investigator after appropriate medical assessment, would pose an unacceptable risk to the patient if they were to continue receiving study drug.

Patients who discontinue study treatment early should receive all early discontinuation procedures as described in Section 2. Patients should be encouraged to remain in the study until Week 52 (Visit 18), even if study treatment has been discontinued, and they should continue to participate in scheduled visits as described in Section 2. Patients who agree to remain in the study after discontinuing study treatment should continue to participate in scheduled visits and assessments, as appropriate, with the exception of PK measurements and PET scans, after completing the early discontinuation assessments described in Section 2, as appropriate. The follow-up visit (Week 56) is not required for patients who discontinue study treatment early and continue in the study, unless the study drug was discontinued within that last 4 weeks of the study. The Lilly-designated medical monitor may be consulted regarding the details of managing a specific patient who discontinues treatment but remains in the study.

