9.2. Adverse Events

Investigators are responsible for monitoring the safety of patients who have entered this study and for alerting Lilly or its designee to any event that seems unusual, even if this event may be considered an unanticipated benefit to the patient.

The investigator is responsible for the appropriate medical care of patients during the study.

Investigators must document their review of each laboratory safety report.

The investigator remains responsible for following, through an appropriate health care option, AEs that are serious or otherwise medically important, considered related to the investigational product or the study, or that caused the patient to discontinue the investigational product before completing the study. The patient should be followed until the event resolves, stabilizes with appropriate diagnostic evaluation, or is reasonably explained. The frequency of follow-up evaluations of the AE is left to the discretion of the investigator.

Lack of drug effect is not an AE in clinical studies, because the purpose of the clinical study is to establish treatment effect.

After the informed consent form (ICF) is signed, study site personnel will record via eCRF the occurrence and nature of each patient's preexisting conditions, including clinically significant signs and symptoms of the disease under treatment in the study. In addition, site personnel will record any change in the condition(s) and any new conditions as AEs. Investigators should record their assessment of the potential relatedness of each AE to protocol procedure and investigational product via eCRF.

The investigator will interpret and document whether or not an AE has a reasonable possibility of being related to study treatment, PET tracers, or a study procedure taking into account the disease, concomitant treatment(s), or concurrent pathologies/conditions.

A "reasonable possibility" means that there is a cause and effect relationship between the investigational product, PET tracers, and/or study procedure and the AE.

The investigator answers yes/no when making this assessment.

Planned surgeries and nonsurgical interventions should not be reported as AEs unless the underlying medical condition has worsened during the course of the study.

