9.4.3. Laboratory Tests

For each patient, laboratory tests detailed in (Appendix 2) should be conducted according to the Schedule of Activities (Section 2).

Any clinically significant findings from laboratory tests that result in a diagnosis and that occur after the patient receives the first dose of investigational treatment or PET tracers should be reported to Lilly or its designee as an AE via eCRF per Section 9.2.

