9.4.6. Safety Monitoring

Lilly will periodically review evolving aggregate safety data within the study by appropriate methods. An AC will be designated for at least one interim evaluation of unblinded safety data from Study LLCF (Section 10.3.7).

If a study patient experiences elevated ALT \geq 3X ULN, ALP \geq 2X ULN, or elevated TBL \geq 2X ULN, hepatic laboratory tests (Appendix 4) must be repeated within 3 to 5 days including ALT, AST, ALP, TBL, direct bilirubin, gamma-glutamyl transferase, and creatine kinase to confirm the abnormality and to determine if it is improving or worsening. If the abnormality persists or worsens, clinical and laboratory monitoring must be initiated by the investigator and in consultation with the study medical monitor. Monitoring of ALT, AST, TBL, and ALP must continue until levels normalize or return to approximate baseline levels.

Additional safety data must be collected via the case report form (CRF) if 1 or more of the following conditions occur:

- Elevation of serum ALT to ≥5X ULN on 2 or more consecutive blood tests
- Elevated serum TBL to ≥2X ULN (except for cases of known Gilbert's syndrome)
- Elevation of serum ALP to >2X ULN on 2 or more consecutive blood tests
- Patient discontinued from treatment due to a hepatic event or abnormality of liver tests
- Hepatic event considered to be a SAE

See Appendix 4, for hepatic eCRFs that must be completed for these patients.

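### AST counts as a stopping criterion in Protocol 8.1.1, but an isolated AST rise triggers no mandatory retest, monitoring or hepatic CRF in 9.4.6 and has no AST-only multiple-of-ULN row in SAP 5.13.4

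*Protocol*

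**What the plan says.** **Stopping criteria.** Protocol 8.1.1 lists seven liver-test conditions under which the investigator should consider stopping study drug. The four that concern aminotransferases all read ALT or AST: above 8X ULN; "alanine aminotransferase or AST >5X ULN for more than 2 weeks"; above 3X ULN with raised bilirubin or prothrombin time; and above 3X ULN with listed symptoms or eosinophilia. Exclusion criterion [27] likewise sets one limit, 2X ULN, for both enzymes.

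**Monitoring.** Protocol 9.4.6 begins: "If a study patient experiences elevated ALT \geq 3X ULN, ALP \geq 2X ULN, or elevated TBL \geq 2X ULN". In that event hepatic tests "must be repeated within 3 to 5 days including ALT, AST, ALP, TBL" and further analytes. If the abnormality persists or worsens, "Monitoring of ALT, AST, TBL, and ALP must continue until levels normalize or return to approximate baseline levels". The only aminotransferase trigger for the additional hepatic CRF is "Elevation of serum ALT to ≥5X ULN on 2 or more consecutive blood tests". AST is measured once another analyte has started the process, but it cannot start it.

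**Analysis.** SAP 5.13.4 counts ALT at 3X, 5X and 10X ULN or more. AST appears at a multiple of ULN only inside the Hy's Law composite, which also needs bilirubin at 2X ULN or more. SAP Appendix 2 nevertheless lists AST at 3X ULN or more as potentially clinically significant.

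**The concern.** A criterion that depends on a rise lasting more than two weeks cannot be judged from one blood sample. For ALT the protocol requires a second sample within days and, if the rise persists, continued monitoring. For an AST rise of the same size without the other abnormalities, it requires neither. A patient could stay on drug with a stopping criterion met but not recognised.

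The reporting issue is separate. An imbalance between arms in marked AST rises without raised bilirubin would have no row comparable with the ALT rows. The treatment-emergent high count does not separate an AST of 1.1X from one of 6X ULN. The amounts that define a notable change are not printed. The liver-disorder AE cluster in SAP 5.13.3 counts only events that were entered as AEs.

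**Working it through.** No figure in the plan needs reproducing. The check sets the sections side by side and measures the gaps in the chemistry schedule.

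**1. Where AST acts as a trigger**

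| Place | Conditions | Conditions an AST value can meet |
|---|---|---|
| 8.1.1, liver-test discontinuation | 7 | 4 |
| 9.4.6, mandatory repeat | 3 (ALT, ALP, TBL) | 0 |
| 9.4.6, hepatic CRF | 5 (ALT, TBL, ALP, discontinuation for liver tests, hepatic SAE) | 0 directly |
| SAP 5.13.4, single-enzyme multiples of ULN | ALT: 3 (3X, 5X, 10X) | AST: 0 |

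An AST rise reaches the hepatic CRF only through discontinuation or a hepatic SAE.

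**2. Which 8.1.1 criteria depend on a retest**

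- AST above 8X, or above 3X with symptoms or eosinophilia, has no duration and can be met at one visit.
- AST above 3X with bilirubin above 2X sets off the 9.4.6 repeat through bilirubin.
- The prothrombin-time alternative needs a test that is in Protocol Appendix 4 but not in the routine panel of Appendix 2.
- Only the two-week criterion needs a second dated AST value.

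The exposed pattern is therefore AST above 5X and up to 8X ULN, with ALT below 3X, ALP below 2X, TBL below 2X, and no listed symptoms or eosinophilia.

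**3. Days to the next date-fixed AST** (Protocol section 2, chemistry row)

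On-treatment draws are at Weeks 2, 4, 8, 12, 16, 20, 24, 36 and 52 (nine), with a follow-up draw at Week 56. Gap = 7 × (next week − this week):

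- Week 2 to 4: 7 × 2 = 14 days
- Weeks 4, 8, 12, 16 and 20 to the next draw: 7 × 4 = 28 days each
- Week 24 to 36: 7 × 12 = 84 days
- Week 36 to 52: 7 × 16 = 112 days
- Week 52 to 56: 7 × 4 = 28 days

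Gaps over 28 days follow two of the nine draws. With visit windows of ±7 days at Weeks 24 and 36 and ±10 days at Week 52:

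- 84 ± (7 + 7) = 70 to 98 days
- 112 ± (7 + 10) = 95 to 129 days

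**4. Dosing inside the gaps** (same schedule, drug-dispensing row)

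Drug is dispensed without scheduled chemistry at Weeks 28 and 32 (two visits) and at Weeks 40, 44 and 48 (three visits), five in all.

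**The case against.** **Other duties cover much of this.** Protocol 9.2 says "Investigators must document their review of each laboratory safety report" and makes the investigator responsible for following important AEs. The AE definition in Appendix 1 includes abnormal laboratory findings. Appendix 4 tests may be ordered for any treatment-emergent hepatic abnormality, and 8.1.1 allows discontinuation for a clinically significant laboratory value. This stands in part: the gaps above are upper limits that apply only if nobody orders an earlier test. But these routes are discretionary. Section 9.2 adds "The frequency of follow-up evaluations of the AE is left to the discretion of the investigator", and 9.4.3 asks for an AE entry only for "Any clinically significant findings from laboratory tests that result in a diagnosis and that occur after the patient receives the first dose". For ALT, ALP and bilirubin the protocol did not rely on discretion.

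**The criteria in 8.1.1 are themselves advisory, and the ALT path fixes no two-week date either.** Both are true. Considering a criterion still requires knowing whether it is met. The difference between the enzymes is the early repeat, the required monitoring and the CRF trigger.

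**The SAP may already count AST at 3X ULN.** The vital-sign and ECG sections take their abnormality limits from the matching appendices, so treatment-emergent high laboratory values might be read as using SAP Appendix 2. The text favours the other reading. Section 5.13.4 ties Appendix 2 to clinically significant changes in ALT, ALP and bilirubin. Its treatment-emergent high count uses low, normal or high status for each analyte, which would include phosphate and uric acid, for which Appendix 2 has no limits. Even on the alternative reading, AST has no 5X or 10X row.

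**The pattern is narrow and the study has ended.** Both are correct, and they limit what can still be changed.

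**Conclusion.** The concern holds. AST has equal standing with ALT in 8.1.1 and exclusion [27], but in 9.4.6 it starts none of the mandatory steps, and SAP 5.13.4 gives it no row of its own at a multiple of ULN. The long retest gap applies after two of nine on-treatment draws: 84 days (70 to 98) after Week 24 and 112 days (95 to 129) after Week 36. It affects one of the four AST criteria.

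This assumes that no unscheduled test is ordered and that ALT, ALP and bilirubin stay below their triggers. The documents do not say how often isolated AST rises occur, so the number of patients affected cannot be estimated. No data are lost, and sample size, power and alpha are unaffected. This is a should-fix point on patient safety and hepatic reporting.

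**What to change.** - **Protocol 9.4.6:** make the repeat trigger ALT or AST at 3X ULN or more, and the hepatic CRF trigger ALT or AST at 5X ULN or more on two or more consecutive tests.
- **SAP 5.13.4:** add AST at 3X, 5X and 10X ULN or more, to mirror the ALT rows, and ALT or AST above 8X ULN, to match 8.1.1. Compare arms by Fisher's exact test, as for the existing hepatic rows.

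**Cost.** The protocol change is two words in each of two triggers, though it needs an amendment. Patients attend every 4 weeks after Week 24, so a repeat draw is practicable. A few extra draws would follow, some for AST rises of non-hepatic origin; the creatine kinase already in the repeat panel helps to identify these. The protocol change helps only while patients are on drug. SAP Version 2 records early termination, so what remains is the four SAP rows, which use data already collected and are allowed by Protocol 10.3.4 as additional safety analyses.

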8.1.2. Temporary Discontinuation from Study Treatment

Treatment can be temporarily discontinued (examples include short-term treatment using a prohibited drug, uncertain AE, and/or hospitalization). Re-starting investigational product is based on the PI's judgment. If temporary discontinuation is due to an AE, it should be reported to the Lilly-designated medical monitor. Temporary treatment discontinuation and re-starting should be documented. The maximum permissible treatment suspension is 4 weeks over the duration of the study. Exceptions may be considered to allow a subject to resume treatment when the temporary suspension period exceeds 4 weeks, after consultation with the Lilly medical monitor.

8.1.3. Discontinuation of Inadvertently Enrolled Patients

If the sponsor or investigator identifies a patient who did not meet enrollment criteria and was inadvertently enrolled, a discussion must occur between the Lilly-designated medical monitor and the investigator to determine if the patient may continue in the study. If both agree it is medically appropriate to continue, the investigator must obtain documented approval from the Lilly-designated medical monitor to allow the inadvertently enrolled patient to continue in the study with or without treatment with investigational product.

8.2. Discontinuation from the Study

Some possible reasons that may lead to permanent discontinuation include:

- enrollment in any other clinical trial involving an investigational product or enrollment in any other type of medical research judged not to be scientifically or medically compatible with this study
- participation in the study needs to be stopped for medical, safety, regulatory, or other reasons consistent with applicable laws, regulations, and good clinical practice (GCP)
- investigator decision
 - o the investigator decides that the patient should be discontinued from the study

- o if the patient, for any reason, requires treatment with another therapeutic agent that has been demonstrated to be effective for treatment of the study indication, discontinuation from the study occurs prior to introduction of the new agent
- patient or study partner decision: requests their withdrawal from the study
- an individual patient enrolled in the study may be discontinued based on a specific AE
 profile, as recommended by the Lilly-designated medical monitor or the Assessment
 Committee, in discussion with the PI

Patients who discontinue the study early will have end-of-study procedures performed at the early discontinuation visit as shown in the Schedule of Activities (Section 2) and should participate in the follow-up visit, 4 to 6 weeks after the last dose of study treatment.

8.3. Lost to Follow-Up

Site personnel, or an independent third party, will attempt to collect the vital status of the patient within legal and ethical boundaries for all patients randomized, including those who did not get investigational product. Public sources may be searched for vital status information. If vital status is determined, this will be documented and the patient will not be considered lost to follow-up.

Lilly personnel will not be involved in any attempts to collect vital status information.

9. Study Assessments and Procedures

Section 2 lists the Schedule of Activities, with the study procedures and their timing (including tolerance limits for timing).

Appendix 2 lists the clinical laboratory tests that will be performed for this study.

Appendix 5 provides a summary of the maximum number and volume of invasive samples, for all sampling, during the study.

Unless otherwise stated in the subsections below, all samples collected for specified laboratory tests will be destroyed within 60 days of receipt of confirmed test results. Certain samples may be retained for a longer period, if necessary, to comply with applicable laws, regulations, or laboratory certification standards.

9.1. Efficacy Assessments

9.1.1. Primary Outcome Assessments

¹⁸F-AV-1451 PET. ¹⁸F-AV-1451 PET scans provide an in vivo measurement of the anatomical distribution and load of paired-helical filament (PHF)-tau pathology in the brain (Xia et al. 2013). Along with amyloid plaques, tau PHF tangles are one of the defining pathological signatures of neuropathologically confirmed AD. Elevated ¹⁸F-AV-1451 binding is increased in AD relative to control subjects and presents in an anatomical distribution consistent with neuropathological Braak staging (Chien et al. 2013). In contrast to amyloid, which becomes elevated many years before the onset of clinical symptoms, tau pathology is more closely associated in time with cognitive and functional decline. The ¹⁸F-AV-1451 assessment involves 2 PET scans, one at baseline and another after 52 weeks of treatment (or upon early discontinuation). The change in ¹⁸F-AV-1451 SUVr between the two PET scans will be the primary outcome measure. The change in ¹⁸F-AV-1451 SUVr will be compared across the treatment groups and to total exposure to LY3202626.

9.1.2. Secondary Efficacy Assessments

Alzheimer's Disease Assessment Scale—Cognitive subscale (ADAS-Cog; Rosen et al. 1984). The ADAS is a rater-administered instrument that was designed to assess the severity of the dysfunction in the cognitive and noncognitive behaviors characteristic of persons with AD. The cognitive subscale of the ADAS, the ADAS-Cog₁₃, consists of 13 items assessing areas of cognitive function most typically impaired in AD, for example, orientation, verbal memory, language, praxis, delayed free recall, and digit cancellation measures (Mohs et al. 1997). The ADAS-Cog₁₃ scale ranges from 0 to 85, with higher scores indicating greater disease severity.

Alzheimer's Disease Cooperative Study—Activities of Daily Living Inventory (ADCS-ADL; Galasko et al. 1997, 2004). The ADCS-ADL is a 23-item inventory developed as a rateradministered questionnaire that is to be answered by the patient's study partner. The ADCS-ADL subset of items (items 7 to 23) for instrumental activities of daily living (ADCS-iADL) will be used as a secondary efficacy measure. The focus in the mild AD dementia population is on

the instrumental activities of daily living (iADL) rather than the basic activities of daily living (bADL), which are thought to be affected in more severe stages of the disease. The range for the iADL score is 0 to 56, with lower scores indicating greater disease severity. For each of the specific items, the study partner is first asked if the patient attempted the ADL during the past 4 weeks. If the patient did attempt the ADL, the study partner is asked to rate the patient's performance level based on a set of performance descriptions. Scores for each item and the overall score for the tool are calculated. The range for the total ADCS-ADL score is 0 to 78.

Integrated Alzheimer's Disease Rating Scale (iADRS). The iADRS comprises scores from the ADAS-Cog and the ADCS-iADL, 2 well-accepted measures in AD research. The iADRS is calculated as a linear combination of the total scores of the ADAS-Cog₁₃ (score range 0 to 85 with higher scores reflecting worse performance) and the ADCS-iADL (score range 0 to 56 with higher scores reflecting better performance). To account for the opposite directionality of the scores, the ADAS-Cog score is multiplied by (-1) in the calculation of the integrated scale. Then a constant (85) is added to anchor the ADAS-Cog at 0. The iADRS score is then calculated by summing the transformed ADAS-Cog₁₃ and the ADCS-iADL, as shown below:

iADRS score = $[-1(ADAS-Cog_{13})+85]+iADL$

The iADRS score ranges from 0 to 141 with lower scores indicating worse performance (Wessels et al. 2015).

